## **11.0 Local Recruitment Methods**

*11.1 Recruitment Process:*

If a potential participant is identified at the Department of Dermatology at the University of Minnesota Clinics and Surgery Center or Maple Grove Clinic, the attending provider will briefly introduce the study and ask if a member of the study team may come in to talk with them. If the potential participant agrees, the investigator and/or study coordinator will describe the study in detail, answer any questions the potential participant may have and describe next steps. All investigators and study staff will be trained in privacy and confidentiality requirements for conducting research at Fairview facilities. Patients who have opted out of research in their medical record will only be approached by clinical staff.

Additionally, public recruitment will be done via the use of flyers in buildings on the University of Minnesota campus. These buildings could include academic buildings, student residences, athletic facilities, and student dining/recreation buildings. The study will also be posted on the University of Minnesota Department of Dermatology website:

<https://med.umn.edu/dermatology/research/clinical>. Additionally, we will attach a PDF of the flyer to email to be sent out to the Dermatology Interest Group listserv.

Participants may self-refer if they become aware of the study through these recruitment materials or word of mouth referrals. Individuals who respond to the recruitment materials will be taken through a phone screening questionnaire. If following the phone screen the potential participant is eligible and interested, the study coordinator will schedule the screening study visit.

*11.2 Identification of Potential Participants:* Potential participants will be identified by the investigators from among patients under their care. Investigators will make the initial contact with potential participants at the time of their clinic visit.

*11.3 Recruitment Materials:* Public recruitment will be done via the use of flyers that include the study and contact information. Tabs will be available at the bottom of the flyer to take if interested. Flyers will be posted in buildings on the University of Minnesota campus. These buildings could include the Malcolm Moos Health Sciences Tower, Phillips-Wangensteen building, Molecular and Cellular Biology building, and Jackson Hall.

*11.4 Payment:*

- Subjects will be given compensation for engagement in the study. Total compensation for subjects is \$30.00. Subjects will receive \$10.00 per

## MEDICAL PROTOCOL (HRP-590)

PROTOCOL TITLE: Effect of mechanical intervention on the scalp microbiome: setting the stage for the future management of cicatricial alopecias

VERSION DATE: 05 August 2023

- visit including the first baseline and concurrent treatment visit, one additional treatment visits, and one follow up visit.
- Parking will be provided for all subjects who elect to participate at the Department of Dermatology at the University of Minnesota in the Phillips-Wangensteen building or Clinics and Surgery Center . The study will be completed at the University of Minnesota Department of Dermatology in the LCRU space, Maple Grove clinic or the Clinics and Surgery Center. Parking vouchers for the Oak Street patient visit parking ramp will be provided to participants at each in-office visit. Parking at the Maple Grove clinic is free of charge and thus parking vouchers will not be provided if the participants elects to participate at that location.

## 12.0 Withdrawal of Participants

- 12.1 Withdrawal Circumstances: Participation in this study is voluntary. Participants are free to withdraw at any time. Investigators may also withdraw participants from the study if participants fail to adhere to the study protocol requirements. Possible withdrawal circumstances may also include: the participant no longer meets the inclusion/exclusion criteria, the participant is lost to follow-up, or it is in the participant's best interest to withdraw from the study, as determined by the PI.
- 12.2 Withdrawal Procedures: Data collection of withdrawn participants will be collected up to the point of withdrawal. Data from withdrawn participants will not be included in the analysis.
- 12.3 Termination Procedures: This study may be suspended or prematurely terminated if there is sufficient reasonable cause. If the study is prematurely terminated or suspended, the PI will promptly inform the IRB and will provide the reason(s) for the termination or suspension. The study team will also notify the participants of the study termination. Data will not be used after termination. Circumstances that may warrant termination or suspension include, but are not limited to:
  - Determination of unexpected, significant, or unacceptable risk to participants
  - Demonstration of efficacy that would warrant stopping
  - Insufficient compliance to protocol requirements
  - Data that are not sufficiently complete and/or evaluable
  - Determination of futility

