## MEDICAL PROTOCOL (HRP-590)

PROTOCOL TITLE: Effect of mechanical intervention on the scalp microbiome: setting the stage for the future management of cicatricial alopecias

VERSION DATE: 05 August 2023

|  |   |
|--|---|
|  | 

• Swab of right and left mid-frontal scalp prior to treatment

• HairMetrix photography before treatment

• Right side of scalp treatment with the Venus Glow™ device and brush (left side will not be treated)

• Swab of right mid-frontal scalp post- treatment

   |
| Beginning of Week 1 - Second Treatment
(+/- 3 days) | 

• Participant report of adverse events

• Swab of right and left mid-frontal scalp prior to treatment

• HairMetrix photography before treatment

• Right side of scalp treatment with the Venus Glow™ device and brush (left side will not be treated)

• Swab of right mid-frontal scalp post-treatment

 |
| End of Week 1- Final Visit (+/3 days)                   | 

• Participant report of adverse events

• Swab of right and left mid-frontal scalp

• HairMetrix photography

  |

All participants will have a final 3-6 day visit and swab collection after their treatments have been completed and they have returned to their typical hair and scalp care routine, described above. All visits including this final visit will be compensated at \$10 per visit. If a patient happens to miss a study visit, one of the study staff will reach out to the patient via a phone call.

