## **15.0 Statistical Considerations**

*15.1 Data Analysis Plan:*

The primary analysis will evaluate whether there is a difference in the baseline and 2-week change in the relative abundance of pre-specified bacteria (approx. 20) between the device-treated portion of the scalp and the non-treated portion. In order to account for the within-subject correlation, mixed-effects models will be performed. As a secondary analysis, we will compare the HairMetrix images and analyze how various demographic and clinical factors such as sex and skin type impact the effect of the device.

*15.2 Power Analysis:*

Limited data are available to inform a power/sample size estimate. However, if there is a total of 38 subjects (40 initial, with 5% dropout), then we will have pre- and post-treatment data for 38 device-treated, and 38 non-treated portions of the scalp. Even when ignoring the within-subject correlation, this will allow us to have 80% power to detect an effect size of 0.7 (difference in the baseline to week 1 change between groups), assuming an alpha of 0.05.

*15.3 Data Integrity:*

- The study monitor will ensure that the investigation is conducted according to protocol design and regulatory requirements. The monitor will provide ongoing monitoring of data validity and regulatory issues (e.g., eligibility determinations, consent form process, serious adverse event reporting, IRB actions, disclosures of conflict of interest).
- Study records will be monitored at regular intervals by the study monitor. The monitor will perform source data verification and as such must be given access to the subject's primary source documentation, such as paper or electronic medical records such as consent to participate in the study, visit dates, demographic information, adverse events, concomitant medications, drug accountability, etc. that support data entries in the CRF.

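### Section 12.2 drops every withdrawn participant from the analysis, although the planned mixed-effects model could use the swabs they have already given; a small, cheap improvement

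*Combined protocol and SAP*

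**What the plan says.** Section 12.2 gives two rules in succession. The first is "Data collection of withdrawn participants will be collected up to the point of withdrawal". The second is "Data from withdrawn participants will not be included in the analysis". No exception is made for the reason or the timing of withdrawal.

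Section 12.1 draws withdrawal widely. Besides the participant's own choice and loss to follow-up, "Investigators may also withdraw participants from the study if participants fail to adhere to the study protocol requirements", and the PI may act where "it is in the participant's best interest to withdraw from the study, as determined by the PI". Loss of eligibility also counts.

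Section 15.1 describes the primary analysis as the "difference in the baseline and 2-week change in the relative abundance of pre-specified bacteria" between the treated and untreated portions of the scalp, and adds: "In order to account for the within-subject correlation, mixed-effects models will be performed". Section 15.2 describes the powered contrast as the "difference in the baseline to week 1 change between groups". Section 15 defines no analysis set, missing-data method or sensitivity analysis that would bring withdrawn participants back.

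The visit table in 5.3 lists, at each of the two treatment visits, "Swab of right and left mid-frontal scalp prior to treatment" and then one right-side swab after treatment. The final visit has one right and one left swab.

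**The concern.** The protocol collects swabs and then rules them out, while planning a type of model that does not need complete participants. A likelihood-based mixed-effects model uses whatever visits a person has, and remains valid if the missing visits depend only on what was observed.

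Two things are at stake. One is precision: in a study now sized at 20-25 people, each person removed is a visible share of the information. The other is interpretation: the result describes only people who were not withdrawn, and the plan does not call for reporting when or why the others left.

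**Working it through.** **Inputs.** Enrolment of 20-25 (5.1); 40 enrolled, 5% dropout, effect size 0.7, alpha 0.05, within-subject correlation ignored (15.2); visit table (5.3). Assumptions of mine: two-sided alpha; correlation 0.3-0.7 between right-minus-left differences at different visits, with equal variances; between-side correlation 0.5 for the paired check.

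**The plan's own figures.** 40 × 0.95 = 38, as stated. A two-sample t-test with 38 per side and d = 0.7 has power 0.853, not 0.80; the effect detectable at 80% is 0.651, which rounds to 0.7. The stated power is thus conservative, and this point does not depend on it.

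**Swabs in hand.** Visits give 3 + 3 + 2 = 8 swabs. Someone leaving after the second visit has given 6, of which 4 form two right/left pre-treatment pairs (baseline and second visit). The other 2 are right-side post-treatment swabs with no left swab at the same time. Someone leaving after the first visit has one such pair and one right-only swab.

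**Expected number leaving.** 0.05 × 20 = 1.0 and 0.05 × 25 = 1.25. If people leave independently, the chance that two or more leave is 26% at 20 and 36% at 25 (binomial).

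**Cost of losing whole people** (d = 0.7, t-test power):

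| Enrolled | Basis | None lost | One lost | Two lost |
|---|---|---|---|---|
| 25 | unpaired | 0.679 | 0.661 | 0.641 |
| 20 | unpaired | 0.578 | 0.556 | 0.532 |
| 25 | paired, assumed 0.5 | 0.919 | 0.907 | 0.894 |
| 20 | paired, assumed 0.5 | 0.844 | 0.823 | 0.799 |

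One person costs 1.8-2.2 points unpaired and 1.2-2.1 paired. Two cost 3.8-4.6 unpaired and 2.5-4.5 paired. These are ceilings on what any change could recover.

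**How much of that comes back.** Take the right-minus-left difference at baseline, second visit and final visit, with variance 1 and common correlation ρ. With n complete people, the variance of a change between two visits is 2(1 − ρ)/n. If m of N people are incomplete, add their information for the visits they have, obtain the generalised least squares variance V, and convert it to an effective number of complete people, 2(1 − ρ)/V. The share recovered is (effective number − (N − m))/m.

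Example: N = 25, m = 1, ρ = 0.5, final minus baseline. Complete people only: 1/24 = 0.04167. Keeping someone with baseline and second visit: V = 0.04111, effective number 24.32, share 0.32. Keeping someone with the baseline pair only: V = 0.04125, effective number 24.24, share 0.24.

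Over N = 20 or 25 and m = 1 or 2, final minus baseline:

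| ρ | Left after second visit | Baseline pair only |
|---|---|---|
| 0.3 | 0.36-0.38 | 0.33-0.34 |
| 0.5 | 0.31-0.32 | 0.23-0.24 |
| 0.7 | 0.27-0.29 | about 0.14 |

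For second visit minus baseline, someone leaving after the second visit has the whole contrast, so the share is 1.00.

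**Product.** With one person leaving after the second visit, final minus baseline: 0.27 × 1.8 = 0.5 points up to 0.38 × 2.2 = 0.8 points. For second visit minus baseline, the full 1.8-2.2 points.

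**The case against.** The strongest case for leaving the rule alone is that some withdrawals ought to remove data. Section 12.1 covers people who break the protocol or lose eligibility. In this study that can mean antimicrobial use (excluded in 8.2) or shampooing or chemical treatment (restricted in 5.2), which may act on the microbiome being measured. Putting swabs taken after such a breach into the primary analysis would be worse than excluding them. This stands, and it narrows the remedy. It does not justify discarding swabs taken before the breach, or those of people who were simply lost to follow-up.

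The plan is also consistent with itself: 15.2 counts only those left after dropout. A reader might infer an error in the power calculation from 12.2; there is none on this point. The rule also reaches only withdrawn people. A missed visit prompts a phone call (5.3) and is not itself listed as withdrawal.

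A reader might also infer that the estimate is biased. Each person is their own control, so exclusion removes both sides together and keeps them balanced. Bias needs withdrawal to be related to response. Individual results are not shared (7.1), so any link would be indirect, for example through the irritation listed in 13.1, and nothing in the protocol shows one.

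Finally, it is tempting to say that 6 of 8 usable swabs are thrown away and that little is lost when someone leaves after the first visit. Neither holds: only 4 of the 6 are same-time pairs, and a baseline pair alone still carries 14-34% of that person's information.

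**Conclusion.** The point holds as a cheap improvement of minor weight. Section 12.2 discards data that the planned model could use. At the plan's 5% dropout, the gain from keeping them is at most about 2 power points, and under 1 point if the contrast is final visit minus baseline.

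Which figure applies depends on a matter the protocol leaves open: 15.1 speaks of two weeks and 15.2 of week 1, and the visit table places both the second treatment and the final visit in week 1. The size also rests on the assumed correlations, on data missing at random, and on a model that takes the swabs of every visit, including baseline, as repeated responses. A model fitted only to a single change from baseline to the final visit would recover nothing for these people. If more people leave than planned, the gain rises accordingly.

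**What to change.** Replace the exclusion sentence in 12.2 with:

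> Swabs collected before withdrawal, and before any eligibility or adherence breach that could affect the scalp microbiome, will be included in the mixed-effects analysis as far as consent allows; the timing and reason of each withdrawal will be reported, and an analysis excluding all withdrawn participants will be a sensitivity analysis.

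The cost is a check that the consent wording (not in the copy reviewed) permits this use, a judgement on the date of any breach made without sight of the sequencing results, and one extra analysis. No swabs or visits are added.

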## 13.0 Risks to Participants

### 13.1 Foreseeable Risks:

Potential risks include scalp irritation, redness, headache, itching, tingling, and abrasion of the skin.

## MEDICAL PROTOCOL (HRP-590)

PROTOCOL TITLE: Effect of mechanical intervention on the scalp microbiome: setting the stage for the future management of cicatricial alopecias

VERSION DATE: 05 August 2023

Privacy/Confidentiality Risks: There is always the slight risk of loss of confidentiality of the medical record information and associated privacy of the participants. These risks will be minimized by storing data securely as per UMN institutional guidelines and limiting access to information contained within the registry to trained UMN investigators and members of the research team.

*13.2 Reproduction Risks: N/A*

*13.3 Risks to Others: N/A*

## **14.0 Potential Benefits to Participants**

*14.1 Potential Benefits: Participants may experience an improvement in scale and/or oiliness of the scalp. Additionally, society and investigators will benefit from the knowledge gained.*

## **15.0 Statistical Considerations**

*15.1 Data Analysis Plan:*

The primary analysis will evaluate whether there is a difference in the baseline and 2-week change in the relative abundance of pre-specified bacteria (approx. 20) between the device-treated portion of the scalp and the non-treated portion. In order to account for the within-subject correlation, mixed-effects models will be performed. As a secondary analysis, we will compare the HairMetrix images and analyze how various demographic and clinical factors such as sex and skin type impact the effect of the device.

*15.2 Power Analysis:*

Limited data are available to inform a power/sample size estimate. However, if there is a total of 38 subjects (40 initial, with 5% dropout), then we will have pre- and post-treatment data for 38 device-treated, and 38 non-treated portions of the scalp. Even when ignoring the within-subject correlation, this will allow us to have 80% power to detect an effect size of 0.7 (difference in the baseline to week 1 change between groups), assuming an alpha of 0.05.

*15.3 Data Integrity:*

- The study monitor will ensure that the investigation is conducted according to protocol design and regulatory requirements. The monitor will provide ongoing monitoring of data validity and regulatory issues (e.g., eligibility determinations, consent form process, serious adverse event reporting, IRB actions, disclosures of conflict of interest).
- Study records will be monitored at regular intervals by the study monitor. The monitor will perform source data verification and as such must be given access to the subject's primary source documentation, such as paper or electronic medical records such as consent to participate in the study, visit dates, demographic information, adverse events, concomitant medications, drug accountability, etc. that support data entries in the CRF.

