### 3.0 Study Endpoints/Events/Outcomes

- 3.1 Primary Endpoint/Event/Outcome: The primary endpoint will be scalp swab assessment of scalp microbiome composition before and after Venus Glow™ treatment. Our hypothesis is that there will be a decrease in microbe burden on the scalp with treatment.
- 3.2 Secondary Endpoint(s)/Event(s)/Outcome(s): Secondary endpoint includes scalp swab assessment of scalp microbiome composition after participants have returned to their normal hair and scalp care routine, providing information about the normal, healthy scalp microbiome. In addition, photography comparisons with the HairMetrix device will be taken before each treatment at the swab sites for each participant.

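### The primary analysis tests about 20 bacteria with no success rule and no multiplicity control, so a claim based on any one of them could carry a false-positive chance of up to about 64%

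*Combined protocol and SAP*

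**What the plan says.** Section 15.1 defines the primary analysis as the "change in the relative abundance of pre-specified bacteria (approx. 20) between the device-treated portion of the scalp and the non-treated portion". On method it says only: "In order to account for the within-subject correlation, mixed-effects models will be performed". It does not say whether there is one model per bacterium or one joint model, and the list of bacteria is not in the document.

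Section 15.2 gives the only alpha, attached to one unnamed outcome: "80% power to detect an effect size of 0.7 (difference in the baseline to week 1 change between groups), assuming an alpha of 0.05". This is for 38 analysed subjects (40 enrolled, 5% dropout), ignoring the within-subject correlation.

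Section 3.1 states the hypothesis: "Our hypothesis is that there will be a decrease in microbe burden on the scalp with treatment". It names no taxon and gives no rule for reading the taxon results against that hypothesis. No section mentions a family-wise or false-discovery adjustment.

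The time point also differs between sections. Section 15.1 refers to a two-week change and 15.2 to a change from baseline to week 1. The last visit in the 5.3 schedule is headed "End of Week 1- Final Visit (+/3 days". After baseline, both sides of the scalp are swabbed before the second treatment and again at that last visit. Section 3.2 makes the swab taken after return to the usual routine a secondary endpoint.

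**The concern.** With about 20 taxa under one primary heading and no rule for combining them, the plan as written allows each to be tested at 0.05 and any that passes to be reported as the primary result. Pre-specifying the list limits which taxa are tested, but it does not control error across them. The mixed model deals with correlation between the two sides of one scalp, which is a different problem.

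The risk is that a chance shift in one bacterium is published as a device effect and carried into the scarring-alopecia work that this study is meant to prepare. The power statement is affected too, because a figure for one comparison at 0.05 does not carry over to some 20 comparisons once they are adjusted.

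**Working it through.** **Inputs from the plan.** About 20 taxa (15.1); alpha 0.05, effect size 0.7, 80% power, 38 treated and 38 untreated portions (15.2); enrolment of 20 to 25 (5.1). Sidedness is not stated; two-sided is assumed because 15.1 asks about a difference.

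**Assumed, not in the plan.** Correlation between tests (rho), correlation between the two sides' changes (r), and the number of taxa that truly change (k).

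**1. The plan's own power figure.** Treating the portions as two independent groups of 38 with effect 0.7 and two-sided 0.05, power is 85.3% (t-test) or 86.2% (normal). The effect detectable with 80% power is 0.651, so the stated 0.7 is consistent with rounding and is conservative. This is the power of one unadjusted comparison.

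**2. Chance of at least one false positive, no taxon changed.** For m independent tests it is 1 - 0.95^m.
- m = 20: 1 - 0.3585 = 0.642
- m = 15: 0.537
- m = 25: 0.723

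For jointly normal two-sided tests the independent case is the maximum under any correlation (Sidak inequality). For 20 equally correlated tests the chance is 1 minus the integral over u of phi(u) × [Phi((1.96 - u√rho)/√(1 - rho)) - Phi((-1.96 - u√rho)/√(1 - rho))]^20:
- rho = 0.3: 0.540
- rho = 0.5: 0.419
- rho = 0.7: 0.289

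**3. The same chance with Benjamini-Hochberg at 5%.** For 20 tests at rho = 0, 0.3, 0.5 and 0.7 it is 5.0%, 4.7%, 4.0% and 3.1%.

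**4. What the adjustment does when some taxa change.** Simulation of 40,000 trials with 20 independent taxa. A paired t-test stands in for the side-by-time contrast, with standardised difference 0.7/√(2(1 - r)): 0.495 at r = 0 and 0.7 at r = 0.5. At 38 subjects and r = 0:

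| Taxa changed (k) | Expected false share of claims, unadjusted | Same, adjusted | Chance of any false claim, unadjusted | Same, adjusted |
|---|---|---|---|---|
| 1 | 40% | 4.8% | 62% | 7% |
| 5 | 13% | 3.8% | 54% | 15% |
| 10 | 5% | 2.5% | 40% | 19% |

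**5. Power per changed taxon.** Unadjusted values are from the noncentral t; adjusted values are from the simulation.

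| Subjects analysed | r | Unadjusted | Adjusted, k = 1 / 5 / 10 |
|---|---|---|---|
| 38 | 0 | 84% | 45 / 61 / 72% |
| 25 | 0 | 66% | 23 / 32 / 42% |
| 20 | 0 | 56% | 15 / 20 / 28% |
| 38 | 0.5 | 99% | 85 / 95 / 97% |
| 25 | 0.5 | 92% | 57 / 75 / 84% |
| 20 | 0.5 | 84% | 41 / 58 / 71% |

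The rows for 25 and 20 assume that everyone enrolled is analysed. Any dropout lowers them.

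**The case against.** This is a small healthy-volunteer study, 15.2 itself says that planning data are limited, and a taxon screen is often read as exploratory. A joint model may have been intended, in which case the problem would not arise. Benjamini-Hochberg is also only one acceptable choice: a single global test or a named lead taxon would serve. If half the taxa truly change, the expected false share without adjustment is already about 5%, so the gain is largest when few or none change.

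All of that is fair, but it does not close the gap. The protocol calls this the primary analysis, states a hypothesis, quotes alpha and power, and nowhere specifies a joint test.

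The simulations also fit the endpoint imperfectly. Relative abundances share one total, so a real change in one taxon moves the shares of others. A state with one taxon changed and 19 independent and exactly null is an illustration only. Likewise, 64% is a ceiling for two-sided tests. One-sided tests with slight negative correlation (-1/19) give about 68%.

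A reader might infer two stronger points that the documents do not support:
- **That both follow-up swabs are open as primary time points, giving 40 tests and a ceiling of 1 - 0.95^40 = 87%.** Section 3.2 makes the return-to-routine swab secondary, and 5.2 and 5.3 place it at the final visit. That leaves the second-treatment visit, which fits the week-1 wording in 15.2. The two changes also share a baseline swab, so they are not independent.
- **That the study could be stopped on a chance result because 12.3 lists "Demonstration of efficacy that would warrant stopping".** This is one item in a general list of termination grounds, and no interim efficacy analysis is described.

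**Conclusion.** The concern holds and should be fixed before analysis. The primary analysis covers about 20 taxa with one alpha of 0.05 and no rule for what counts as positive. The chance of a false primary claim is at most about 64%, on four conditions: any one unadjusted result may be claimed, tests are two-sided and jointly normal, there are 20 of them, and no taxon changes. The number of taxa and the correlation between tests move that figure, but even at an assumed correlation of 0.7 it is 29%, about six times the nominal 5%.

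The 64% is not a prediction for this trial. It shows what the wording permits. The differing time points in 15.1, 15.2 and 5.3 need reconciling, but they do not justify doubling the number of primary tests.

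**What to change.** **In 15.1, before analysis:**
- List the taxa.
- State one mixed model per taxon with one primary contrast: treated minus untreated side, change from baseline.
- Name one time point, reconciling 15.1, 15.2 and the 5.3 schedule, and note that 3.2 makes the return-to-routine swab secondary.
- State that Benjamini-Hochberg control of the false-discovery rate at 5% applies across the list, and that only adjusted results count as positive primary findings.

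**In 15.2:** state that the 80% power is for one unadjusted taxon at 38 subjects.

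**Cost.** A few sentences and one line of analysis code, with no change to visits, swabs or sequencing. The real price is power per taxon, and it is steeper at the 20 to 25 subjects in 5.1 than at 38. If the two sides' changes are uncorrelated, adjusted power at 25 subjects is about 23% to 42% for 1 to 10 changed taxa; at an assumed correlation of 0.5 it is about 57% to 84%. The method limits the share of false claims, not the chance of any, so some risk of a single false claim remains when several taxa truly change. The change also leaves the link between the taxon results and the burden hypothesis in 3.1 still to be stated.
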